Vitamin D has been shown as an important marker of prognosis in a variety of clinical settings, including overall mortality, acute respiratory distress syndrome (ARDS), infection/sepsis, asthma, cardiovascular disease, diabetes, and pediatric/medical/surgical intensive care unit outcomes. Vitamin D not only plays a role in bone maintenance, but also a variety of extra-axial functions including immune-dysregulation and systemic inflammation. In addition, a number of randomized clinical trials support the supplementation of vitamin D as improving outcome in critical care patients. While the evaluation of vitamin D levels remains a standard-of-care at our institution, the widespread use of vitamin D monitoring and impact on neurocritical care patients remains limited. Our recent prospective observational study of vitamin D levels in neurocritical patients showed that deficiency (<20ng/ml) was highly associated with prolonged hospital stay and increased in-hospital mortality for emergent patients. Moreover, a number of limitations arise from this study due to its observational nature. **This study proposes a randomized, double-blinded, placebo-controlled, single center evaluation of vitamin D supplementation in the neurocritical care patient population (Table 1). Patients admitted to the neurocritical care unit for emergent cases and with vitamin D deficiency (<20ng/ml) will undergo vitamin D serum draw on admission and be randomized to receive cholecalciferol/vitamin D3 supplementation (540,000 IU once orally) or placebo with the primary measured outcome being hospital length-of-stay.** Secondary outcomes will include length of hospital course, length of ICU course, complications, adverse events, discharge Glasgow Outcome Score, in-hospital and 30-day mortality, as well as quality-of-life. Power analysis estimates 198 patients will be needed for each subgroup to determine a 2 day difference in length-of-stay, and we plan to recruit 218 patients per treatment arm to account for dropout, which will take approximately 6-9 months to recruit. Interim analysis and safety monitoring will be performed. We hypothesize that vitamin D supplementation may make a significant impact on reducing morbidity and mortality in the neurocritical care population. The possibility of reducing hospital length of stay and mortality from a simple and cheap intervention such as vitamin D supplementation may be a useful adjuvant treatment in the neurocritical care population.

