2. Background/Rationale

Hypovitaminosis D has a high prevalence among the general population, with some studies showing over half of the elderly population being affected (Chapuy 1997). Among critically ill patients, various studies have shown associations between hypovitaminosis D and multiple negative outcomes including mortality (De Haan 2014,

Rech 2014), ARDS (Dancer 2015), and infection (Flynn 2012). Vitamin D deficiency has also been shown to have impacts on various neurological diseases such as stroke (Yalbuздag 2015, Chung 2015), and dementia (Littlejohns 2014). While the mechanism between vitamin D deficiency and these diseases is not entirely known, evidence suggest that vitamin D can affect vascular reactivity, inflammation, and the immune system (Carthy 1989, Vargas-Vasserot 2011) (Table S1, Figure S1-2).

Vitamin D has been shown to impact prognosis in a variety of retrospective and randomized clinical trials within an intensive care unit (ICU) environment (Amrein 2011). **Despite these findings, there have been no studies examining the impact of hypovitaminosis D in specialized neurocritical care units (NCCU).** Given the often significant differences in the management of patients in NCCU and more generalized intensive care units (Kurtz 2011) there is a need for further inquiries into the impact of low vitamin D levels in this specific environment. **This study proposes a randomized, double-blinded, placebo-controlled, single center evaluation of vitamin D supplementation in the emergent NCCU patient population (Table 1).** We have previously conducted a prospective, observational analysis of 823 NCCU patients and shown a significant reduction in hospital length-of-stay for all patients (7.14 vs. 5.97 days, $p=0.0018$) and for emergent cases (8.21 vs. 6.36 days, $p=0.038$), as well as reduced in-hospital mortality for emergent patients with non-deficient vitamin D levels (26/203 vs. 22/321, $p=0.021$). Nevertheless, these results remain limited in being observational studies without randomization or controls.

3. Study purposes and objectives

1. Evaluate the impact of vitamin D supplementation on the length-of-stay of emergent neurocritical care patients (primary outcome)
2. Evaluate the impact of vitamin D supplementation on in-hospital mortality, ICU length-of-stay, Glasgow Outcome Score on discharge, complications, and quality-of-life metrics (secondary outcome)

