4.8. Selection of therapeutic agent

Patients will be supplemented with cholecalciferol (vitamin D3) or placebo. Two major vitamin D compounds exist in humans, ergocalciferol (vitamin D2) and cholecalciferol (vitamin D3) and recent guidelines suggest that either vitamin D2 or vitamin D3 can be supplemented in patients with hypovitaminosis D (Holick 2011). One study evaluating short-term supplementation with vitamin D2 in an critical care setting demonstrate that only 26% of patients receiving 50,000 IU three times per week achieved normal vitamin D levels (Dickerson 2015). Critically ill patients have been suggested to have a blunted response to vitamin D supplementation. Nonetheless, a number of randomized trials have shown the ability of high dose vitamin D3 to adequately replete critically ill patients with minimal toxicity, mostly mild hypercalcemia (Quraishi 2015, Nair 2015, Amrein 2011, Amrein 2014). Intramuscular (200,000 IU) or oral (540,000 IU) have been shown to adequately replete vitamin D levels in the majority of patients by 2-7 days after treatment. For this reason we have chosen to supplement with cholecalciferol (540,000 IU orally).

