4.9. Power analysis and statistical plan

A variety of variables will be collected on patients (Table 2). We estimated various sample sizes based on our preliminary, prospective, observational trial. Using length-of-stay as a primary outcome, previously we detected a significant decrease in patients with sufficient vitamin D levels ($>20\text{ng/ml}$) (8.21 vs. 6.36 days, $p=0.002$). Using an effect size of 2, alpha of 0.05, 1:1 case/control sampling, we estimate 198 patients will be required per group for this study. We plan to recruit patients to account for a 10% dropout resulting in 218 patients per group, total 436. We also performed power calculations using various other outcomes including, in-hospital mortality, as well as evaluation of both emergent and non-emergent patients. Based on a 6-month timeframe needed to enroll 512 patients in our prospective, observational trial, we estimate the trial would take 12 months for enrollment and randomization in the proposed trial. The primary outcome (length-of-stay) will be measured by T-test as well as multivariate regression to adjust for potential confounders using SPSS (IBM, Armonk, NY). Secondary outcomes will be evaluated by a variety of statistical methods.

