4.10. Funding source

Planned sources of funding for this study are from internal departmental grants without potential for conflicts-of-interest. No submission for additional funding sources is planned at this time.

5. Anticipated results and potential public health impact

The potential benefit of this study would include knowledge about the success of vitamin D supplementation on various critical care outcomes. While they may not directly apply to a patient, they can be useful to additional critical care patients admitted an ICU in the future. The societal benefit will include reduced patient morbidity and mortality, as well as shorter hospital stays and therefore reduced ICU expenditure. Vitamin D is a relatively cost-effective medication that is well-tolerated. Its potential impact to reduce hospital stays, by even 1 day would play a significant role in reducing patient cost, disease morbidity, and risk from hospitalization. Future research directions can involve a multi-center randomized clinical trial to validate the effect of vitamin D in the neurocritical care patient as well as further molecular studies evaluating the non-skeletal effects of vitamin D. Additional, studies on vitamin D as a biomarker and effects on a cellular level can also be forthcoming if a potential benefit is identified clinically. Identification of the molecular mechanisms by which vitamin D may alter disease pathology may serve as a method for the development of additional treatments.

6. Protocol amendments

6.1. 1/10/17, Addition of phone consents as well as two study co-investigators, [name] and [name] was performed. Repeat vitamin D levels at 3 days following administration of study drug or placebo was modified from prior planned repeat vitamin D at 7 days.

6.2. 8/6/17, Addition of physical therapy assessment and modified Rankin scale as secondary outcomes of the study. Change of study faculty sponsor from [name] to [name] as [name] is leaving the University of Utah.

Table 1: Summary of Study Characteristics	
Title	Randomized Clinical Trial of Hypovitaminosis D Treatment in the Neurocritical Care Unit
Methodology	Randomized, double-blinded, placebo-controlled clinical trial
Study Duration	1-1.5 years (12 months recruitment, 3-6 month analysis)
Study Center(s)	University of Utah Health Sciences Center

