Aygenel 2013	Prospective cohort	201	Increased mortality in vitamin D deficient (<20ng/mL) patients (43 vs. 26%) Increase rates of severe acute disease, worsened laboratory studies on admission, morbidity and exposure to invasive therapy in deficient patients.
Su 2013	Prospective cohort	206 (105 ICU) Normal vs. ICU sepsis	Lower vitamin D seen in patients with ICU sepsis compared to normal patients No difference in mortality with vitamin D levels
Amrein 2014	RCT	475, (patients with deficiency ≤ 20 ng/ml) Placebo vs. 540,000 IU x1, monthly 90,000 IU for 5 month	No difference in mean hospital stay (19.3 vs. 20.1), hospital mortality (35.3% vs. 28.3%), 6-month mortality (42.9% vs. 35.0%) Severe vitamin D subgroup (n=200) showed no difference in hospital stay (19 vs 20.1 days) and 6-month mortality (50% vs. 34.7%) Severe vitamin D subgroup showed significantly lower hospital mortality (46.1% vs. 28.6%, p=0.04),
Moromizato 2014	Retrospective cohort, two-center	3,386 Normal vs. insufficiency vs. deficiency	Preadmission vitamin D deficiency was predictive for risk of sepsis including after adjustment for other variables 90-day mortality was 1.6x higher in patients with preadmission vitamin D insufficiency and deficiency (HR. 1.63)
Dickerson 2015	Retrospective cohort	65 50,000 IU qweek, Blweek, Tlweek for 4 weeks	Normal vitamin D levels achieved in 6%, 11% and 26% of patients
Brook 2015	Retrospective cohort	300 Normal vs. deficient	Vitamin D levels showed an inverse correlation with non-home discharge destination
Nair 2015	RCT	50 150,000 IU vs.	65% vs. 67% of patients normalized vitamin D levels by 7

		300,000 IU vitamin D3 IM	days 80% vs. 83% of patients normalized vitamin D levels by 14 days Secondary hyperparathyroidism manifest in 25% of patients
Alizadeh 2015	Retrospective cohort	70 Normal vs. deficient	Longer length of stay (7.8 vs. 4.05 days) with deficient patients but no difference in hospital mortality
Quraishi 2015	RCT	30 Placebo vs. 200,000 IU cholecalciferol vs. 400,000 IU cholecalciferol	Plasma levels of vitamin D peaked on day 5 of treatment CRP levels did not differ between groups
Verceles 2015	Retrospective cohort	183 Normal vs. deficient	Deficiency was common (61% patients) and not associated with days to wean from ventilation

[figure not shown]

Figure S1: Forest plot of 30-day mortality in studies with univariate analysis of vitamin D sufficiency vs. deficiency. Adapted from de Haan et al. 2014.

[figure not shown]

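### Is 198 per group undermined because it is sized on 2 days, above the 1.85-day pilot difference and the 1 day mentioned in Section 5, with no SD or power given?

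*Combined protocol and SAP*

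**What the plan says.** Section 4.9 takes its planning data from the centre's observational study and reads: "8.21 vs. 6.36 days, $p=0.002$). Using an effect size of 2, alpha of 0.05, 1:1 case/control sampling, we estimate 198 patients will be required" in each group. Adding 10% for dropout gives 218 per group and 436 in total. The opening summary supplies the unit that Section 4.9 leaves out: "Power analysis estimates 198 patients will be needed for each subgroup to determine a 2 day difference in length-of-stay". The primary analysis is a t-test, with multivariate regression for adjustment.

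Four other places bear on the size of effect to expect:

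- Section 2 gives the same pilot contrast a different p-value, "for emergent cases (8.21 vs. 6.36 days, $p=0.038", and says of the pilot findings that "these results remain limited in being observational studies without randomization or controls".
- Section 4.8 says of the intramuscular and oral doses it cites that they "have been shown to adequately replete vitamin D levels in the majority of patients by 2-7 days after treatment".
- Table S1 lists a 475-patient randomized trial ("Placebo vs. 540,000 IU x1, monthly 90,000 IU for 5 month") with the result "No difference in mean hospital stay (19.3 vs. 20.1), hospital mortality (35.3% vs. 28.3" percent.
- Section 5, on anticipated results and public health impact, says: "Its potential impact to reduce hospital stays, by even 1 day would play a significant role in reducing patient cost".

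The document states no SD for length of stay, no target power and no sidedness.

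**The concern.** The target difference looks optimistic in every direction. It exceeds the observed pilot difference. That difference comes from comparing deficient with non-deficient patients, so treatment would reproduce it in full only if the association were causal and repletion came early in the stay. A larger randomized trial with the same loading dose saw no difference in stay. Section 5 also says that half the target would matter.

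Because sample size varies with the inverse square of the difference, a target that is too large makes a trial too small. Without an SD or a power, a reader cannot tell whether 198 has room for a smaller effect. The risk is that a non-significant t-test is taken to mean that supplementation does not work, when the trial could not have excluded a useful benefit.

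**Working it through.** **Inputs.** Pilot means 8.21 and 6.36 days, design difference 2, alpha 0.05, 1:1 allocation and 198 per group (Section 4.9). Unit of days (opening summary). Emergent group sizes 203 and 321 (mortality denominators, Section 2). SD, power and sidedness are not given. I assume a two-sided test and 80, 85 or 90% power.

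**1. The plan's own steps.** 198 × 1.1 = 217.8, so 218; 2 × 218 = 436. Both agree with the text. The 198 cannot be reproduced without an SD. Read as 2 SD units, the difference would need only 4 to 6 patients per group, so 2 must mean days.

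**2. SD implied by 198.** From n = 2(z₁₋α/₂ + z_power)²(SD/d)², SD = d√(n/2)/(z₁₋α/₂ + z_power). With d = 2 and n = 198:

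- 80%: 2 × 9.950/2.802 = 7.10 days
- 85%: 2 × 9.950/2.996 = 6.64 days
- 90%: 2 × 9.950/3.242 = 6.14 days

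The document gives no SD that contradicts these values.

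**3. Sample size for other differences.** With SD, power and sidedness held fixed, n scales as (2/d)². For 8.21 − 6.36 = 1.85 days: 198 × (2/1.85)² = 231.4, so 232. For 1 day: 198 × 4 = 792.

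**4. Power at smaller differences.** Power ≈ Φ[(1.96 + z_power)(d/2)√(n/198) − 1.96]. For example, at 80% with d = 1.85 and n = 198: Φ(2.802 × 0.925 − 1.96) = Φ(0.63) = 0.74. A noncentral-t calculation gives the same rounded figures.

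| Power at 2 days with 198 | 1.85 days, n = 198 | 1.85 days, n = 218 | 1 day, n = 198 | 1 day, n = 218 | 95% CI half-width, n = 198 |
|---|---|---|---|---|---|
| 80% | 74% | 78% | 29% | 31% | 1.40 days |
| 85% | 79% | 83% | 32% | 35% | 1.31 days |
| 90% | 85% | 88% | 37% | 40% | 1.21 days |

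The columns for 218 matter because length of stay is known at hospital discharge, so loss after discharge need not reduce the number analysed. Safety withdrawals under Section 4.4 could still remove some patients.

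**5. Is 2 just 1.85 rounded?** Suppose p = 0.002 came from a two-sided pooled t-test on 203 and 321 patients. Then t = 3.106, SE = 1.85/3.106 = 0.596 and SD = 0.596/√(1/203 + 1/321) = 6.64. At 80% power this SD needs 203 per group for 1.85 days and 174 for 2 days. The stated 198 is closer to the first, so the calculation may have used the pilot difference, with 2 a rounding in the text. This cannot be confirmed.

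**6. Can the pilot p-values stand in for the missing SD?** Not safely. Taken the same way, p = 0.038 gives SD 9.92 and 52% power for 2 days at 198 per group. But Section 2 also reports 7.14 vs 5.97 days with p = 0.0018 for all 823 patients. As a pooled t-test, that gives t = 3.13, SE = 1.17/3.13 = 0.374 and an SD of at most 0.374 × √(823/4) = 5.36, so a within-group sum of squares of at most 821 × 5.36² ≈ 23,600. The emergent patients alone would need 522 × 9.92² ≈ 51,400, which is impossible if they are a subset. With p = 0.002 they need 522 × 6.64² ≈ 23,000, which leaves almost nothing for the other patients. So p = 0.038 cannot be an unadjusted pooled t-test on these numbers, and p = 0.002 is doubtful as one.

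**The case for a change.** The strongest case for a change is that this is the sample-size basis of the primary outcome and nobody outside the team can check it. The stated difference departs from the pilot in the direction that makes the trial smaller. The plan's own evidence (an uncontrolled pilot, repletion in most but not all patients, a larger randomized trial with no difference) points below 1.85 days rather than above it. Under the assumed scenarios, a result of exactly zero would have a 95% interval of about ±1.2 to ±1.4 days and would not exclude the one day named in Section 5.

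The facts and the arithmetic stand. The missing SD, power and sidedness are a real gap in reporting, and the two p-values conflict. The inference to a change does not stand, for these reasons:

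- The plan states no power, so there is no declared target that the design can be shown to miss.
- Section 5 describes public-health impact and looks ahead to a multi-center trial to validate the effect. It sets no minimal important difference. Measuring the design against 1 day imposes a target that the plan did not choose.
- The Table S1 trial had stays of 19.3 and 20.1 days, against 8.21 and 6.36 in the pilot, and added monthly doses. Section 2 argues that neurocritical care differs from general intensive care. The trial counsels caution but does not fix the effect to expect here.
- Nowhere does the plan say that a non-significant result will be reported as no benefit. The mean difference and standard error behind the t-test also give the confidence interval, and a careful analyst would report it.

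**Conclusion.** No change to the plan. The gap between 2 and 1.85 days is 0.15 day. It costs about 5 to 6 points of power at 198 per group, or leaves power about 2 points below nominal if all 218 contribute. This assumes that 198 was set for 80 to 90% two-sided power at 2 days. Sizing on 1.85 days would take 232 per group before dropout. With the plan's own 10% addition that is 255 per group (232 × 1.1 = 255.2, rounded to the nearest patient), or 510 in total: 74 more than the planned 436, for a difference that may be rounding. A single-center trial aimed at an effect of pilot size is a fair trade-off, and the 792 per group for 1 day answers a question that the plan did not set.

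The unstated SD, power and sidedness are inputs the team can supply from its own pilot data. Supplying them would alter neither the randomization, the enrolment, nor the estimate and interval that the trial will report. The conflict between p = 0.002 and p = 0.038 is clerical, since neither is named as an input to the calculation. The conclusion would be different if the pilot data showed an SD near 9.9 days, where 198 per group gives only 52% power for 2 days. The one reported p-value that points there cannot be an unadjusted pooled t-test on the stated numbers if the emergent patients are part of the 823.

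### The protocol's planning figures disagree: two recruitment periods, two p-values for one pilot comparison, and a dropout allowance that falls just short of its target

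*Combined protocol and SAP*

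**What the plan says.** **Recruitment.** The abstract says of the 436 patients, "which will take approximately 6-9 months to recruit". Section 4.9 says "Based on a 6-month timeframe needed to enroll 512 patients in our prospective, observational trial, we estimate the trial would take 12 months", and Table 1 also allows 12 months for recruitment.

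**Pilot result.** Section 2 describes an "observational analysis of 823 NCCU patients". It reports length of stay for all patients as "7.14 vs. 5.97 days, $p=0.0018" and "for emergent cases (8.21 vs. 6.36 days, $p=0.038". In-hospital mortality in emergent patients, deficient against non-deficient, is "26/203 vs. 22/321, $p=0.021". Section 4.9 repeats the emergent means with another p-value: "8.21 vs. 6.36 days, $p=0.002$). Using an effect size of 2, alpha of 0.05, 1:1 case/control sampling, we estimate 198 patients". No test is named for any of the length-of-stay p-values. The t-test in section 4.9 is the planned analysis of the new trial.

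**Sample size.** The abstract makes clear that the effect of 2 is in days: "Power analysis estimates 198 patients will be needed for each subgroup to determine a 2 day difference in length-of-stay". No SD, power or sidedness is given anywhere. Section 4.9 then allows for 10% dropout and arrives at 218 per group, 436 in all.

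**The concern.** These figures justify randomising 436 critically ill patients at one centre, and the reader cannot tell which of them to believe. Two recruitment periods are stated, and the shorter one looks hard to reach because the trial takes only patients below 20 ng/ml, whereas the accrual base is quoted without any reduction for deficiency. A timeline that is too short risks a trial that stops below its target.

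The two p-values matter because the SD is missing. A reader who wants to check 198 has only the pilot p-values to work back from, and 0.038 and 0.002 imply quite different SDs.

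**Working it through.** **1. Recruitment**

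Inputs: 436 patients and 512 per 6 months (section 4.9); 203 deficient and 321 non-deficient emergent pilot patients (section 2, mortality denominators).

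The share of the accrual base that must be deficient, eligible and consenting, with no assumption about deficiency:
- 6 months: 436/512 = 85.2%
- 9 months: 436/768 = 56.8%
- 12 months: 436/1024 = 42.6%

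Pilot emergent deficiency rate: 203/(203+321) = 203/524 = 38.7%. Applying it to the 512 is an assumption: the protocol does not describe them, and 512 equals neither 524 nor 823.

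| Period | Base | Deficient at 38.7% | Shortfall against 436 |
|---|---|---|---|
| 6 months | 512 | 198 | 238 |
| 9 months | 768 | 298 | 138 |
| 12 months | 1024 | 397 | 39 |

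(That 198 also equals the per-group sample size is coincidence.) Time to 436 at full uptake: 436/(512/6 x 0.387) = 436/33.06 = 13.2 months.

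Over the 95% Wilson interval for 203/524 (34.7-43.0%), 9 months yields 266-330, 12 months yields 355-440, and reaching 436 takes 14.7 down to 11.9 months. The interval covers sampling error only, not whether the rate carries over. All these counts are before refusals and exclusions.

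**2. Pilot p-values and the 198**

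The 198 cannot be reproduced from the stated inputs. Solved backwards for a 2-day difference, two-sided 0.05, it corresponds to an SD of 7.09, 6.63, 6.12 or 5.51 days at 80, 85, 90 or 95% power (one-sided: 7.99, 7.41, 6.79, 6.04).

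Now assume pooled two-sided t-tests, with the mortality denominators serving for length of stay. Emergent difference: 8.21 - 6.36 = 1.85 days; SD = (1.85/t)/sqrt(1/203 + 1/321), where the square root is 0.0897.
- p=0.038: t = 2.080, SD = 9.92
- p=0.002: t = 3.106, SD = 6.64

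Section 2's all-patient result tests these. Difference: 7.14 - 5.97 = 1.17 days; p=0.0018 on 821 df gives t = 3.13. The split of the 823 is not given; an equal split gives the largest possible SD, 5.36 (5.42 allowing for rounding of the printed figures).

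If the emergent patients are a subset of the 823, their within-group sum of squares cannot exceed that of all patients. Hence emergent SD <= 5.36 x sqrt(821/522) = 6.72 (6.80 with rounding).

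At that cap, t = 1.85/(6.72 x 0.0897) = 3.07, so the emergent p is at most 0.0023 (0.0025 with rounding). Conversely, an emergent SD of 9.92 needs an all-patient SD of at least 9.92/sqrt(821/522) = 7.91, which gives an all-patient p of at least 0.034, not 0.0018.

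Power at 198 per group for 2 days, two-sided 0.05: 84.0% at SD 6.72 and 83.1% at SD 6.80.

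**3. Dropout**

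198 x 1.10 = 217.8, which reproduces 218. But 218 x 0.90 = 196.2, below 198; keeping 198 after a 10% loss needs 198/0.90 = 220. The loss that 218 does cover is 20/218 = 9.2%. Power at 196 is 83.6% at SD 6.72 and 82.8% at SD 6.80, under 0.5 percentage points lower.

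**The case against.** The case for leaving the plan alone has real force. A p-value is not an input to the stated calculation, which uses 2 days, alpha 0.05 and 1:1 allocation, so the conflict does not itself change the design. On the pooled t-test reading the value that fails is in the background section, not in the sample-size paragraph. The missing SD, power and sidedness are then a reporting gap. All of this stands.

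On recruitment, two of three statements agree on 12 months, and Table 1's six-month interim analysis sits consistently half-way through that period. The projections depend on a deficiency rate borrowed for 512 undescribed patients. Section 4.7 lets other ICUs contribute, although section 4.3 expects most patients from the NCCU. Section 4.5 says many patients will lack capacity to consent, but it also provides for proxy and telephone consent. So the projections are conditional; the contradiction between the abstract and the other two places is not.

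Inflating by 1.10 is a common convention, and its effect here is trivial.

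A reader might draw two stronger conclusions. One is that the trial is underpowered: taken alone, p=0.038 gives SD 9.92 and about 52% power. Section 2's own all-patient result rules out that SD under the same assumptions. The other is that 0.002 is merely the all-patient 0.0018, rounded and misplaced. The rounding matches, but the bound shows that 0.002 fits the emergent data and 0.038 does not, so the documents do not support that explanation.

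**Conclusion.** The point holds as a set of internal contradictions that should be fixed. It does not show that the sample size is too small.

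- **Recruitment.** The abstract contradicts section 4.9 and Table 1 outright. Conditional on a 38.7% deficiency rate among the 512, 6-9 months is not supported, and 12 months is about 39 patients short even at full uptake (13.2 months needed) unless other ICUs contribute. This does not show that 12 months is impossible: the top of the interval just reaches 440, with almost everyone enrolled.
- **Pilot p-values.** Two values 19-fold apart are attached to one comparison. If they are pooled t-tests on 203 and 321 patients drawn from the 823, 0.038 is the inconsistent one. If another test was used, neither p-value yields an SD and the bound does not apply.
- **Power.** The 83-84% at the SD cap describes a pilot-like population. It is not a guaranteed minimum for this trial, which requires deficiency and an expected ICU stay of 48 hours or more; the documents do not say that the pilot's emergent group met those conditions.
- **Dropout.** Minor: 2 patients per arm below the stated need.

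**What to change.** 1. Give one recruitment period in the abstract, section 4.9 and Table 1. Derive it from a defined accrual base and explicit deficient, eligible and consenting fractions, counting other ICUs if they are relied on.
2. Recheck the emergent length-of-stay result in the pilot data, name the test, and make sections 2 and 4.9 agree. In the same edit, state the SD, power and sidedness behind 198; if the SD does not support 198, restate the power or the detectable difference.
3. Keep 218 per group and describe the dropout allowance as about 9%.

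The cost is a recheck of data that the investigators should already hold, and a few lines of text. The downside is that the stated timeline will probably lengthen.
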